### 9.2 Sample Size and Accrual

Each cohort will use a Simon two-stage design.

For Cohort A: The disease control rate (DCR: CR+PR+SD) at 4 months on this regimen is expected to be 65%. A Simon two-stage minimax design with an alpha=0.05, and power of 80% will be used. The null and alternative hypothesis DCRs are 40% and 65%, respectively. The null hypothesis of 4-month DCR of 40% is based on data from Kaplan Meier analysis from a previous phase III study [11]. In the first stage, 12 evaluable patients will be enrolled and treated. If 5 or less of these 12 patients are either a CR, PR, or SD at 4 months, the trial will be suspended and the PI will consult with the trial sponsors and the DSMC on whether or not to continue to investigate the treatment regimen further. If 6 or more are either a CR, PR, or SD at 4 months, then another 14 evaluable patients will be accrued for a total of at least 26 evaluable patients. If a total of 15 (or more) of these patients are either a CR, PR, or SD at 4 months, then the treatment regimen for this cohort would be considered of clinical interest and would therefore justify further development.

For Cohort B: The disease control rate (DCR: CR+PR+SD) at 4 months on this regimen is also expected to be 60%. The null and alternative hypothesis DCRs for this cohort are 33% and 60%, respectively. The null hypothesis of 4-month DCR of 33% is based on data from a retrospective analysis of a subgroup of patients rechallenged with cetuximab monotherapy among patients who initially had disease control/response with anti-EGFR therapy, among whom median PFS was 4.90 months [29]. Given that this was a retrospective study with a highly selected group of patients, we believe a reasonable null hypothesis of 4-mo DCR of 0.33 is a reasonable extrapolation. In the first stage, 10 evaluable patients will be enrolled and treated. If 3 or less of these 10 patients are either a CR, PR, or SD at 4

months, the trial will be suspended and the PI will consult with the trial sponsors and the DSMC on whether or not to continue to investigate the treatment regimen for this cohort further. If 4 or more are either a CR, PR, or SD at 4 months, then another 11 evaluable patients will be accrued for a total of at least 21 evaluable patients. If a total of 11 (or more) of these patients are either a CR, PR, or SD at 4 months, then the treatment regimen for this cohort would be considered of clinical interest and would therefore justify further development.

We expect the study accrual for both cohorts to take approximately 14 months.

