### 1.3 **Cetuximab**

In 2004, the U.S. Food and Drug Administration approved the first monoclonal antibody targeting the epidermal growth factor receptor (EGFR), cetuximab. Cetuximab significantly improves progression-free and overall survival (PFS and OS) compared to best supportive care in *KRAS* codon 12 and 13 wild-type metastatic CRC patients,[11] and more recent data indicates benefit is limited to those wild-type in *KRAS* and *NRAS* at exons 2, 3, and 4 [12]. Moreover, the presence of a *BRAF* mutation is a marked negative prognostic factor, although there are conflicting reports on whether patients who have *BRAF* mutant CRC benefit from cetuximab [13]. Nevertheless, for the approximately 40% of metastatic CRC patients who have tumors wild-type in *KRAS*, *NRAS*, and *BRAF* [14], and are thus eligible for treatment with anti-EGFR therapy, ultimately disease progression does occur. Thus, novel therapies and combinations are urgently required. Although a wide variety of resistance mechanisms have been

identified, they generally result in aberrant activation of downstream or alternative signaling components through mutation or amplification, resulting in reactivation of ERK signaling and its downstream pathways [15, 16]. The addition of other targeted therapies that synergize with cetuximab will likely mitigate the development of resistance and prolong the duration of benefit with anti-EGFR therapy.

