### 4.1 Inclusion Criteria

- 4.1.1** Written informed consent obtained to participate in the study and HIPAA authorization for release of personal health information.
- 4.1.2** Age  $\geq$  18 years at the time of consent.
- 4.1.3** ECOG Performance Status of 0-2
- 4.1.4** Histologically-confirmed metastatic CRC
- 4.1.5** Measurable disease according to RECIST v1.1 for solid tumors.
- 4.1.6** Documented wild-type in KRAS and NRAS (codons 12, 13, 59, 61, 117, and 146) and in BRAF codon 600, based on tumor tissue taken from primary or metastatic site and tested for biomarkers
- 4.1.7** Previously treated with at least two prior regimens of systemic chemotherapy for metastatic or locally advanced, unresectable disease, including fluoropyrimidines (5-fluorouracil and/or capecitabine), oxaliplatin, and irinotecan.
  - A maintenance regimen of 5-fluorouracil or capecitabine, with or without bevacizumab, should not be counted as a separate line of treatment
  - For patients who experienced disease recurrence during or within 6 months of completion of adjuvant chemotherapy with fluoropyrimidine and oxaliplatin, only one regimen of systemic chemotherapy for metastatic disease is required
- 4.1.8** Demonstrate adequate organ function as defined in the table below; all screening labs to be obtained prior to initiating study medications.

System	Laboratory Value
Hematological*	
Hemoglobin (Hgb)	$\geq 9$ g/dL
Absolute Neutrophil Count (ANC)	$\geq 1500/\text{mm}^3$
Platelets	$\geq 100,000/\text{mm}^3$
Renal*	

Creatinine OR Calculated creatinine clearance	$\leq 1.5 \times \text{ULN}$ $\geq 60 \text{ mL/min}$ by Cockcroft-Gault formula
Hepatic*	
Bilirubin	$\leq 1.0 \times \text{upper limit of normal (ULN)}$
Aspartate aminotransferase (AST)	$\leq 3 \times \text{ULN}$ OR $\leq 5 \times \text{ULN}$ (if liver metastases present)
Alanine aminotransferase (ALT)	$\leq 3 \times \text{ULN}$ OR $\leq 5 \times \text{ULN}$ (if liver metastases present)

\*Note: Hematology and other lab parameters that are  $\leq$  grade 2 BUT still meet criteria for study entry are allowed. Furthermore, changes in laboratory parameters during the study should not be considered adverse events unless they meet criteria for dose modification(s) of study medication outlined by the protocol and/or worsen from baseline during therapy.

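### Cohort A's 40% null is not matched to the KRAS/NRAS/BRAF wild-type patients enrolled, and the 15/26 rule has almost no slack if cetuximab alone does better than 40%

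*Combined protocol and SAP*

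**What the plan says.** Section 9.2 sets the Cohort A benchmark in one sentence: "The null hypothesis of 4-month DCR of 40% is based on data from Kaplan Meier analysis from a previous phase III study [11"]. It does not say which arm or molecular stratum of that study was read, at what precision, or whether the figure was adjusted. The design is then built on it: "A Simon two-stage minimax design with an alpha=0.05, and power of 80% will be used", and "The null and alternative hypothesis DCRs are 40% and 65%, respectively". At stage 1, "If 5 or less of these 12 patients are either a CR, PR, or SD at 4 months, the trial will be suspended"; otherwise "then another 14 evaluable patients will be accrued for a total of at least 26 evaluable patients". Success is defined by "If a total of 15 (or more) of these patients are either a CR, PR, or SD at 4 months", and the regimen is then held to merit further development.

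Two other places bear on the 40%:

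- Section 1.3 cites reference [11] for the benefit of cetuximab over best supportive care in patients wild-type at KRAS codons 12 and 13. It goes on: "more recent data indicates benefit is limited to those wild-type in" both KRAS and NRAS at exons 2 to 4. It also calls BRAF mutation a marked negative prognostic factor.
- Criterion 4.1.6 requires "Documented wild-type in KRAS and NRAS (codons 12, 13, 59, 61, 117, and 146) and in BRAF codon 600".

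For Cohort B, section 9.2 does discuss how its historical source was selected, and calls the 33% null an extrapolation. It offers no such reasoning for Cohort A.

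**The concern.** As the protocol describes it, the population tied to reference [11] could include patients with KRAS mutations outside codons 12 and 13, NRAS mutations or BRAF mutations. This trial excludes them, and section 1.3 says they gain nothing from cetuximab or have a poor prognosis. Taking a worse-faring subgroup out of an average raises the average of those who remain. A 40% rate carried over unchanged would then be too low as a stand-in for cetuximab alone in Cohort A.

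This matters because Cohort A has no control arm. The null is the only thing that separates an effect of palbociclib from what cetuximab would do by itself in anti-EGFR-naïve patients. If the null is too low, cetuximab with an inactive partner can reach 15 of 26 more often than the stated 5%, and the result would be credited to the combination.

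**Working it through.** **Inputs from section 9.2.** Null 0.40; alternative 0.65; n1 = 12; stop at 5 or fewer; n = 26; success at 15 or more. Alpha is taken as one-sided, since sidedness is not stated, and the stage 1 stop is treated as binding.

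**Formula.** For a true 4-month disease control rate p,

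P(success | p) = Σ over x = 6 to 12 of P(Bin(12, p) = x) × P(Bin(14, p) ≥ 15 − x).

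**Step 1: reproduce the plan.** At p = 0.40 the terms for x = 6 to 11 are

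0.1766×0.0583 + 0.1009×0.1501 + 0.0420×0.3075 + 0.0125×0.5141 + 0.0025×0.7207 + 0.0003×0.8757 = 0.047.

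The x = 12 term is negligible. Unrounded, alpha is 0.0469. At p = 0.65 the sum is 0.809. An exhaustive search for 40% versus 65% returns this same design as the minimax solution, so the plan's arithmetic is right.

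**Step 2: keep the rule and vary the true cetuximab-alone rate.** These rates are assumptions.

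| True rate with an inactive partner | P(success) |
|---|---|
| 40% | 0.047 |
| 42% | 0.071 |
| 43% | 0.086 |
| 45% | 0.123 |
| 48% | 0.197 |
| 50% | 0.257 |

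Solving P(success | p) = 0.05 gives p of about 0.403. A true rate 0.3 percentage points above the null uses up the whole allowance.

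**Step 3: illustrate how a shift could arise.** Let f be the share of the source population with the other RAS or BRAF mutations, and d their 4-month disease control rate. Suppose also that 40% is the unadjusted average. The rate in the remaining patients is then p = (0.40 − f·d)/(1 − f). The documents give neither f nor d, so these are examples only:

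- f = 10%, d = 30%: (0.40 − 0.03)/0.90 = 41.1%, P(success) 0.059
- f = 10%, d = 20%: (0.40 − 0.02)/0.90 = 42.2%, P(success) 0.074
- f = 20%, d = 20%: (0.40 − 0.04)/0.80 = 45.0%, P(success) 0.123
- f = 25%, d = 10%: (0.40 − 0.025)/0.75 = 50.0%, P(success) 0.257

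Over f from 5% to 30% and d from 0% to 30%, the rate runs from 40.5% to 57.1% and P(success) from 0.053 to 0.527. The direction is the same throughout, but the size is essentially undetermined.

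**The case against.** The strongest reply is that nothing has been miscalculated. Alpha is defined at the stated null, and there it is 0.047. Dependence on a historical benchmark is common to all single-arm trials. This stands: the point concerns how well the benchmark fits the population, not an error in the design calculation.

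A reader might infer that cetuximab alone must exceed 40% in this trial. The documents do not support that. Section 9.2 does not say which arm or stratum gave the 40%, or whether it was already adjusted. Section 1.3 reports a benefit in codon 12/13 wild-type patients; it does not say that the study enrolled only such patients. Performance status, prior lines of treatment, and the difference between a Kaplan-Meier estimate and response status at 4 months in evaluable patients could move the rate either way. None of these can be compared here. Section 1.3 also notes conflicting reports on whether BRAF-mutant patients benefit from cetuximab. The argument needs only their worse prognosis, which section 1.3 states, but a very low rate for them is less certain.

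The consequence is also tempered. The primary objective is estimation, section 9.3 promises 95% confidence intervals, and at exactly 15/26 an ordinary exact interval (ignoring the two stages) is about 37% to 77%. A reader could see that 45% or 50% is not excluded. But the go/no-go decision in section 9.2 rests on the count, not the interval, so the point survives.

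**Conclusion.** The concern holds as a question of benchmark fit. By the protocol's own account, molecular selection alone pushes the cetuximab-alone rate in Cohort A above the rate in the population tied to reference [11], and no adjustment or justification is given. Other things equal, a rate above 40% is to be expected; how far above is not in the documents.

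What can be said exactly is how sensitive the rule is: 0.047 at 40%, above 0.05 from about 40.3%, then 0.123 at 45% and 0.257 at 50%. The figures for 45% and 50% are a sensitivity range and should not be read as a corrected alpha. They rest on a binding stage 1 stop, a one-sided test and assumed true rates.

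**What to change.** In section 9.2, with 26 patients and both cut-offs unchanged:

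1. State which arm and stratum of reference [11] gave the 40%, and whether it was rounded or adjusted.
2. Re-derive the null for KRAS/NRAS/BRAF wild-type patients, or justify keeping 40% for them. Reference [13], whose title covers PIK3CA, BRAF and PTEN, may help with BRAF. Nothing in the documents shows that it can supply an extended-RAS figure.
3. Report the false-positive rate of the 5/12, 15/26 rule for nulls from 40% to 50%, as in the first table under the working.
4. Read the conclusion that the regimen merits further development against that range, not against 40% alone.

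The cost is wording and a less favourable stated error rate; no patients are added. Raising the final cut-off is not part of this fix because it costs power. Against a 45% null, 16/26 gives alpha 0.064 with power 0.71 at 65%, and 17/26 gives 0.029 with power 0.57.

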### **9.3 Data Analysis Plans**

DCRs and ORRs for both cohorts will be reported with their 95% confidence intervals. PFS and OS will be estimated using the Kaplan-Meier method. Toxicity and safety information will be reported in a descriptive manner in the form of frequency tables. Hypothesis generating [REDACTED], in the form of logistic and Cox regression, designed to investigate potential associations between the outcomes of response rates, such as DCR and ORR, and of PFS and OS, between selected tumor mutations and pharmaco-dynamic biomarkers of interest will be performed when appropriate sample size considerations allow.

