## 1.0 BACKGROUND AND RATIONALE

### 1.1 Study Synopsis

We will conduct a multicenter, single-arm, phase II clinical trial of combination therapy with cetuximab and palbociclib in refractory *KRAS*, *NRAS*, and *BRAF* wild-type metastatic colorectal cancer (CRC) patients. Cohort A will include anti-EGFR naïve patients, and Cohort B will include patients previously treated with an anti-EGFR therapy that experienced at least 4 months of disease control (ie, CR, PR or stable disease) with their prior anti-EGFR therapy and received their last anti-EGFR therapy at least 8 weeks prior to the first dose of study drug. Cohort B is limited to the subpopulation of patients previously exposed to anti-EGFR therapy who may benefit from rechallenge with anti-EGFR therapy. The primary endpoint is 4-month disease-control rate upon treatment with the combination of palbociclib and cetuximab in adults with refractory *KRAS/NRAS/BRAF* wild-type metastatic CRC. We hypothesize that this combination will improve the 4-month disease-control rate in patients with refractory *KRAS/NRAS/BRAF* wild-type metastatic colorectal cancer (CRC) who are either naïve to EGFR therapy (Cohort A) or eligible for rechallenge (Cohort B). Up to 26 subjects will be enrolled in cohort A and up to 21 subjects will be enrolled in cohort B.

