## 9.0 STATISTICAL CONSIDERATIONS

### 9.1 Study Design

This will be a prospective, multicenter, phase 2 study containing two separate but parallel cohorts, of a treatment regimen that involves the combination therapy of cetuximab and palbociclib in refractory KRAS, NRAS, and BRAF wild-type metastatic colorectal cancer patients. Cohort A will include anti-EGFR naïve patients, and Cohort B will be of patients previously exposed to anti-EGFR therapy, but who may be able to benefit from a re-challenge with this anti-EGFR therapy. The primary objective of each cohort is the estimate the disease control rate (DCR: CR, PR or SD) at 4 months. Secondary objectives include estimating the overall response rate (ORR: CR or PR) at 4 months, progression free survival (PFS), overall survival (OS) and the toxicity and safety profile in each cohort.

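### Does the planned 95% confidence interval for disease control contradict the success rule when a cohort only just succeeds?

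*Combined protocol and SAP*

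**What the plan says.** Section 9.1 frames the aim as estimation: "The primary objective of each cohort is the estimate the disease control rate (DCR: CR, PR or SD) at 4 months". Section 9.2 gives each cohort a Simon two-stage design. For Cohort A it adds: "A Simon two-stage minimax design with an alpha=0.05, and power of 80% will be used". The nulls and alternatives are 40% against 65% in A and 33% against 60% in B. A cohort goes to stage 2 with at least 6 of 12 (A) or 4 of 10 (B) patients under disease control. At the end, the rule for A begins "If a total of 15 (or more) of these patients are either a CR, PR, or SD at 4 months" and the rule for B begins "If a total of 11 (or more) of these patients are either a CR, PR, or SD at 4 months"; a cohort that meets its rule is considered of clinical interest.

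Section 9.3 then deals with reporting: "DCRs and ORRs for both cohorts will be reported with their 95% confidence intervals". It names no interval method, mentions no adjustment for the two stages, and does not tie the interval to the decision.

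**The concern.** The estimate and its interval are what a reader of the results will see first. If Cohort A ended at 15/26 or Cohort B at 11/21, the report would call the regimen worth developing while the only planned interval still covered the rate set as uninteresting. That looks as if the analysis undercuts the decision. It would also invite someone to choose a more flattering interval after the fact. The natural response is to ask for a second interval built to agree with the rule, such as a 90% interval adjusted for the two stages. If the interval were in fact the test, success would need one more responder than 9.2 says, and the stated power would be wrong.

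**Working it through.** **1. Reproduce the design (inputs from 9.2).** With stage-1 size n1, stage-1 stopping bound r1, total n and success cut s,

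P(success | p) = Σ over x from r1+1 to n1 of b(x; n1, p) · P(X2 ≥ s − x), with X2 ~ Bin(n − n1, p).

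| | n1 | r1 | n | s | P(success) at null | P(success) at alternative |
|---|---|---|---|---|---|---|
| A | 12 | 5 | 26 | 15 | 0.0469 (40%) | 0.809 (65%) |
| B | 10 | 3 | 21 | 11 | 0.0496 (33%) | 0.812 (60%) |

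A full search for the minimax design at one-sided 5% and 80% power returns exactly these designs. At one-sided 2.5% it returns n = 32 (A) and n = 26 (B). So the unstated sidedness, and Cohort B's unstated alpha and power, can be recovered: one-sided 5% and 80% in both.

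**2. Intervals at the minimum success count.** The exact (Clopper-Pearson) lower limit solves P(X ≥ s | n, p) = 0.025. Lower limits of the 95% interval:

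| Method | A, 15/26 = 57.7% (null 40%) | B, 11/21 = 52.4% (null 33%) |
|---|---|---|
| Clopper-Pearson | 36.9% | 29.8% |
| Wilson | 38.9% | 32.4% |
| Wald | 38.7% | 31.0% |
| Jeffreys | 38.7% | 31.9% |
| Two-stage-adjusted | 37.3% | 30.0% |

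Every one lies below its null, so the observation is correct.

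**3. Why this happens.** The two-stage one-sided p-value at the minimum count is 0.0469 (A) and 0.0496 (B). Both fall between 0.025 and 0.05. A rule at one-sided 5% accepts them; a two-sided 95% interval, which cuts at 2.5% per side, does not. One success higher, the p-values are 0.0206 and 0.0192, both under 0.025, and the exact lower limits rise to 40.6% (16/26) and 34.0% (12/21), above the nulls. The mismatch is a difference of level and touches one count per cohort.

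**4. How often.** The probability of ending exactly on the cut under the alternatives is 0.1015 (A) and 0.1257 (B). As a share of declared successes that is 0.1015/0.8086 = 12.6% and 0.1257/0.8117 = 15.5%.

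**5. Is the planned interval itself sound?** I enumerated all outcomes of the two-stage design for true rates from 30% to 80%, using the interval at n1 for cohorts that stop. Coverage of the exact 95% interval is 94.5–98.7% (A) and 95.0–99.1% (B). Ignoring the two stages does no material harm.

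**6. Would a matched interval be a clear gain?** Lower limits of 90% intervals:

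| 90% interval | A at 15 | A at 14 | B at 11 | B at 10 |
|---|---|---|---|---|
| Two-stage-adjusted | 40.3% | 37.1% | 33.04% | 29.1% |
| Clopper-Pearson | 39.8% | 36.2% | 32.8% | 28.6% |
| Wilson | 41.8% | 38.2% | 35.2% | 31.0% |
| Jeffreys | 41.7% | 38.0% | 35.0% | 30.7% |

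The adjusted interval does agree with the rule on both sides of the cut, but in B by only 0.04 percentage points. Unadjusted Wilson and Jeffreys intervals agree too, with more room though without an exact guarantee. Choosing among them is a matter of presentation.

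**The case for a change.** The best argument for acting is that landing on the cut is not remote: about one declared success in eight (A) or one in six (B), if the alternatives are true. Estimation is the primary objective, and naming a matching interval in advance would cost two or three sentences. All of that is true. It supports an optional line of explanation; it does not show that anything in the plan is wrong.

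The proposed interval also fits the written rules loosely. It treats the stage-1 stop as binding, whereas 9.2 suspends the cohort and leaves continuation to consultation. If cohorts always continued, the type I error would be 0.0518 (A) and 0.0520 (B), and the agreement would no longer be assured. It would also fail in B if the null were read as one third, where the type I error is 0.0531.

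Agreement further needs no more than 26 and 21 evaluable patients. Section 9.2 says "then another 14 evaluable patients will be accrued for a total of at least 26 evaluable patients" and "then another 11 evaluable patients will be accrued for a total of at least 21 evaluable patients", while the synopsis in 1.1 says "Up to 26 subjects will be enrolled in cohort A and up to 21 subjects will be enrolled in cohort B". With 27 or 22 evaluable and the same cuts, the type I error becomes 0.064 or 0.068. That would be a question about the cut, and no interval matched to one-sided 5% could answer it.

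The interval method, the sidedness and Cohort B's alpha and power are indeed not written out. The reproduction in step 1 settles the last two, and the 95% result is the same for every method checked.

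**Conclusion.** The concern does not hold. Section 9.2 decides by count, and the counts have the error rate and power they were designed for. Section 9.3 reports a 95% interval to describe precision and nowhere asks it to exclude the null. The two use different levels, one-sided 5% and two-sided 95%, and so disagree at exactly one count per cohort: 15/26 and 11/21. Following the plan as written gives a valid decision and an interval with adequate coverage; a second interval would alter neither.

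This rests on three things: reading the design as one-sided 5% in both cohorts, which its exact reproduction supports; following the stage-1 rule; and having 26 and 21 evaluable patients in cohorts that complete stage 2.
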